Specifically, meaning is viewed as both an intermediary outcome, as well as a mediator of changes in these important psychosocial outcomes. Religious faith is not expected to directly impact psychosocial outcomes, but may moderate the intermediary outcome of meaning (see, for example, Nelson et al., 2002, indicating that religious faith does not provide a unique contribution to enhanced psychosocial outcomes after controlling for spirituality). This model also presumes that other factors will impact response to a meaning-based intervention, including prognostic awareness, psychosocial treatment preference, and therapeutic alliance. We recognize that the directionality of many of the variables included in this model could potentially be bi-directional; however, we are presenting the model we believe underlies the intervention.

Figure 2: Study Model – Mediators and Moderators of Treatment Outcome

Spiritual Well-Being/meaning and Its Impact on Psychosocial Outcomes in Advanced Cancer

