11.0 BIOSTATISTICS

This project involves a parallel-arm randomized controlled clinical trial to compare the efficacy of three psychotherapy interventions: 1) Individual Meaning-Centered Psychotherapy (IMCP); 2) Supportive Individual Psychotherapy (ISP); and 3) Enhanced Usual Care arm (EUC). We plan to recruit altogether 414 patients (138 in each arm) with solid tumors with advanced disease. The primary outcomes include assessments of meaning (LAP-R), spiritual well-being (FACIT-Sp) and psychological distress (HADS, SAHD, HAI, MQOL).

Omnibus MANOVA for the primary aim:

The general paradigm for assessing the outcomes will be multivariate analysis of variance (MANOVA). MANOVA is appropriate because the primary psychosocial outcomes are highly correlated. The MANOVA method essentially combines the multiple dependent variables together into a weighted linear combination of canonical variates. The canonical coefficients provide the weights in this linear combination. The canonical weights have several advantages. The main advantage is that they inform the relative contribution of each outcome to the overall canonical function (i.e., whether or not meaning contributes more than spiritual well-being to the overall canonical function). MANOVA was chosen, rather than, for example, a mixed-effects modeling approach, primarily because of these considerations. In MANOVA, the combined canonical variate is analyzed in a manner similar to a univariate ANOVA.

The primary aim of this study will be evaluated in one omnibus, one-way MANOVA model against the null hypothesis that all three randomized arms entail comparable post-intervention outcomes in meaning, spiritual well-being, and psychological distress. Thus, the dependent variables will be the six primary outcome assessments (LAP-R, FACIT-Sp, HADS, SAHD, HAI, and MQOL) measured at the post-intervention time point (week 7). The sole independent variable is the randomized intervention assignment. Dunlop, Cortina, Vaslow & Burke (1996) showed that this method provides the most generalizable findings, findings that do not depend on the patients' baseline scores or other baseline characteristics. Thus, the omnibus MANOVA will test whether or not the psychotherapy groups differ in all six correlated outcomes of interest.

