Output:	Noncentrality parameter λ	= 20.8000000
	Critical F	= 2.9936309
	Sample size	= 104
	Actual power	= 0.8062691
	Pillai V	= 0.1666667

A sample size of 104 per randomization arm (138 at baseline) at post-intervention would accommodate a post-intervention attrition rate of up to 25%, which is within the attrition rate in our pilot IMCP trial. The estimated sample size at the follow-up time point (week 15) is 90 participants per intervention condition.

Based on our current IMCP Group psychotherapy intervention, we are currently recruiting at a rate of 5 – 6 individuals to participate. This study involves the IMCP individual therapy, which is more flexible in terms of enrolling patients quickly and scheduling for starting of the therapy sessions. Thus we are confident that we will be able to recruit at a rate of 8 – 9 individuals per month and complete the total enrollment of 414 within the 4-year recruitment period.

Data analytic plans for the secondary aims

To examine clinical and demographic variables that may correspond to differential responses to Individual Meaning-Centered Psychotherapy (e.g., potential moderating influences such as gender, race/ethnicity, religiosity, level of pre-intervention social support, optimism, physical symptom burden, prognostic awareness, and treatment dose).

We anticipate that several socio-demographic and clinical variables will moderate the impact of IMCP. For example, we expect that level of religiosity (based on the IE-12) at the baseline/pre-intervention assessment will be inversely related to treatment response (i.e., less religious individuals will be more likely to experience benefits from this intervention than more religious individuals). We also predict that level of social support will moderate improvement, with those patients reporting higher levels of social support receiving the greatest benefits (because of the emphasis on connectedness to others as a source of meaning in the IMCP intervention). On the other hand, we expect that patients with poorer physical functioning (e.g., lower Karnofsky score), greater pain severity and overall symptom burden (MSAS Global Distress Index scores) will be less likely to benefit from the interventions, in part because unmanaged physical symptoms may impede participation.

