To explore whether an enhanced sense of meaning —explains (mediates) improved psychological well-being (i.e., increased quality of life, decreased psychological distress):

This mediation analysis will be carried out using a MANCOVA model. The dependent variables will be the changes in psychosocial outcomes at the follow-up assessment time point (week 15 minus baseline) in quality of life and psychological distress as a function of intervention condition, adjusting for the post-intervention change in meaning (post-intervention LAP-R minus baseline LAP-R). Thus, the follow-up outcomes will be predicted by enhanced sense of post-intervention meaning. This lagged analysis is necessary because there is a potential confounding effect, for example, in using the post-intervention changes in meaning in predicting post-intervention quality of life. The lagged analysis between follow-up outcomes in quality of life and psychological distress and post-intervention changes in meaning preserves a plausible temporal ordering of causes and effects.

Intent-to-treat analyses and handling of missing data:

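### The lagged mediation model keeps the baseline-to-week-7 outcome change it was meant to avoid, so it does not secure temporal ordering and can show mediation when there is none

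*Combined protocol and SAP*

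**What the plan says.** Section 11.0, under the third secondary aim, specifies a MANCOVA. Its dependent variables are the "changes in psychosocial outcomes at the follow-up assessment time point (week 15 minus baseline") in quality of life and distress. Arm is the factor, and the model is fitted "adjusting for the post-intervention change in meaning (post-intervention LAP-R minus baseline LAP-R").

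The plan explains why the outcome is taken later than the mediator: "there is a potential confounding effect, for example, in using the post-intervention changes in meaning in predicting post-intervention quality of life". It concludes that the lagged version "preserves a plausible temporal ordering of causes and effects".

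Three things are absent:
- The week-7 (T3) outcome is not a covariate, although Section 7.1 schedules MQOL, HADS, SAHD and HAI at T1, T2, T3 and T4.
- No indirect effect, interval or decision rule for mediation is given. The mediation-methods references are cited under the moderator aim.
- The only baseline adjustment is a general rule, also under the moderator aim, that adds the baseline score if it correlates significantly with change.

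**The concern.** The lag moves the end of the outcome window but not its start. The outcome runs from baseline to week 15 and so covers the whole baseline-to-week-7 window in which the LAP-R change is measured. The part the plan itself regards as confounded is still inside the outcome, and nothing in the model takes it out.

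At stake is the explanatory claim of the trial. Section 3.0 presents enhanced meaning as the mechanism of benefit, and Section 2.1 makes it a named aim. An ordinary same-time correlation between meaning and mood at week 7, carried forward to week 15, could be reported as temporally ordered mediation.

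**Working it through.** **Inputs**
- Outcome and mediator windows: Section 11.0, mediation paragraph.
- Sample size: "The estimated sample size at the follow-up time point (week 15) is 90 participants per intervention condition".
- Correlation between the changes: no figure is given. Section 11.0 says only that "MANOVA is appropriate because the primary psychosocial outcomes are highly correlated", and LAP-R is one of those outcomes. Assumed 0.2 to 0.3, with 0 to 0.5 as the wider range.
- Persistence of change: pilot Table 1, Section 3.0, IMCP arm.
- Alpha: none stated for mediation (the 0.01 belongs to the primary MANOVA). Assumed 0.05.

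The plan gives no power or effect size for this analysis, so there is no figure of its own to reproduce.

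**Step 1: the overlap.** T4 − T1 = (T3 − T1) + (T4 − T3). Hence

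Cov(LAP-R T3−T1, Y T4−T1) = Cov(LAP-R T3−T1, Y T3−T1) + Cov(LAP-R T3−T1, Y T4−T3).

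The first term on the right is the concurrent association. Only the second is lagged.

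**Step 2: how much of the change falls in the overlap.** Pilot IMCP means:

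| Measure | T1 to post | Post to follow-up | T1 to follow-up |
|---|---|---|---|
| Quality of life | 7.18 − 5.89 = +1.29 | 6.88 − 7.18 = −0.30 | +0.99 |
| Hopelessness | 4.70 − 7.57 = −2.87 | 4.84 − 4.70 = +0.14 | −2.73 |
| Anxiety | 2.24 − 2.39 = −0.15 | 2.16 − 2.24 = −0.08 | −0.23 |
| Depression | 1.98 − 2.09 = −0.11 | 1.89 − 1.98 = −0.09 | −0.20 |

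Quality of life kept 0.99/1.29 = 77% of its gain and hopelessness 2.73/2.87 = 95%. For these two, the entire follow-up gain arose in the overlapping window. For anxiety and depression the share was 0.15/0.23 = 65% and 0.11/0.20 = 55%. These are group means from another trial, whose hopelessness scale was the BHS rather than the HAI, so they indicate persistence only roughly.

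**Step 3: size of a spurious indirect effect.** Work in SD units of change. Let the arm shift both week-7 changes by d, let those changes correlate at ρ through a common cause, let a fraction r persist to week 15, and let meaning have no effect on outcome. Then a = d and b = rρ. The apparent indirect effect is rdρ out of a total rd, a share of ρ. With r = 0.77, d = 0.5 and ρ = 0.3: 0.77 × 0.5 × 0.3 = 0.116 of 0.385, or 30%. Simulation gave 0.116 of 0.388.

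**Step 4: false-positive rates when meaning has no effect on outcome.** Two arms of 90, d = 0.5, r = 0.77:

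| ρ | LAP-R coefficient, plan | Four-outcome MANCOVA, plan | Joint test of both paths, plan | LAP-R coefficient, adjusted for T3 outcome, T1 outcome and T1 LAP-R |
|---|---|---|---|---|
| 0.1 | 18% | 27% | 16% | 4% |
| 0.2 | 50% | 81% | 46% | 5% |
| 0.3 | 84% | 99% | 77% | 5% |
| 0.5 | 100% | 100% | 92% | 6% |

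A second generating model used three arms of 90, with autocorrelation 0.6 from T1 to T3 and 0.7 from T3 to T4. At ρ = 0.2 / 0.3 the LAP-R coefficient was falsely significant in:
- 33% / 64% with uncorrelated baselines;
- 88% / 98% with baseline correlation 0.4;
- about 52% / 87% with T1 outcome and T1 LAP-R added;
- 4 to 6% after T3 adjustment.

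With only two arms and uncorrelated baselines the coefficient rates fall to about 22% / 48%. With an arm effect of 0.4 on meaning, the joint test ranged from 20% (two arms, ρ = 0.2, uncorrelated baselines) to about 85% across these settings.

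**Step 5: when the problem vanishes or shrinks.**
- Uncorrelated changes and uncorrelated baselines: 5%. With baseline correlation 0.4 and no baseline covariates, the coefficient still reaches 33% at ρ = 0.
- Week-7 change fully lost by week 15: 5%.
- No arm effect on meaning: joint test 0 to 6%. At d = 0.2, ρ = 0.3 and r = 0.77 it is about 24%.
- Measurement error with correlated baselines, ρ = 0.3: plan 65% for the coefficient and 49% for the joint test; T3-adjusted 7 to 8%.

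**Step 6: a tempting shortcut fails.** Using T4 − T3 as the outcome gives 23% at ρ = 0.3 with 77% retained, with the wrong sign.

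**The case against.** The aim is exploratory, and the plan claims only a plausible ordering. Section 3.0 concedes that "the directionality of many of the variables included in this model could potentially be bi-directional". LAP-R at T3 is measured before the T4 outcome, so the order of measurement is right. All of this stands and limits the severity, but the order of the changes is still not secured.

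The LAP-R coefficient is only one of the two paths. Without an arm effect on meaning, a joint test stays at 0 to 6%. If the rule also required a significant total arm effect and the arm truly had none on outcome, false declarations fell to 1 to 4%. This stands too, but the plan states no such rule, and the trial expects IMCP to raise meaning and improve outcomes.

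The conditional baseline rule might be read as covering this model. Even applied always, it leaves about 52% / 87% at correlations of 0.2 / 0.3.

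The strongest objection concerns the remedy. Adjusting for the T3 outcome changes the question. When true mediation was simulated as complete by T3 (path 0.5, no confounding), the T3-adjusted model found it in about 5% of trials, no better than chance, against 74% for the planned model's joint test. The pilot pattern in quality of life and hopelessness suggests that much of the effect may be complete by then. The T3-adjusted model should therefore accompany the planned one, not replace it.

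**Conclusion.** The point holds in conditional form. The overlap is a matter of algebra and needs no assumption: the lag does not remove the component the plan calls confounded. The false signal needs three conditions: week-7 changes in meaning and outcome correlated for a non-mediating reason, persistence to week 15, and an arm effect on meaning. The documents make each credible but quantify only persistence, and that from the pilot. The ranges of 33 to 98% (coefficient, three-arm model) and 20 to 85% (joint test) rest on assumed correlations of 0.2 to 0.3, the assumed baseline correlation and adjustment, 90 per arm and alpha 0.05.

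A reader might infer that the analysis will report mediation whatever the truth, or that the coefficient rates are rates of false mediation. The documents support neither: they give no correlation between changes and no mediation rule, and the coefficient is only one path. A reader might also infer that the two change scores share a baseline score. They share a visit; LAP-R and the outcomes are different instruments.

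This is a secondary, exploratory aim. The primary result is unaffected, but the mediation analysis should be amended before it is used to support the trial's theory.

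**What to change.** - Keep the planned model as a description of association, with T1 outcome and T1 LAP-R always included as covariates.
- Add a companion model of the T4 outcome on arm and T3 LAP-R, adjusted for T3 outcome, T1 outcome and T1 LAP-R.
- Report the indirect effect (arm to LAP-R times LAP-R to outcome) with a bootstrap interval, separately for IMCP vs ISP and IMCP vs EUC. State the alpha and the decision rule.
- Claim temporal ordering only from the T3-adjusted model. Add a sensitivity analysis for unmeasured confounding and for measurement error in the T3 outcome.
- State that the companion captures only mediation operating after T3, so a null result there does not rule mediation out.
- Optionally add a T2-to-T3 model as a sensitivity analysis. Exclude patients whose post-intervention value is substituted from T2, as Section 11.0 allows for those too sick to finish; for them the interval is empty.

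The cost is analysis-plan wording and some analysis time. Every visit and measure needed is already scheduled.

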Following informed consent, patients will be assigned a subject number and randomized to one of the two 7 session interventions (IMCP vs ISP) or to the EUC control condition. Randomization will be completed by MSKCC's Department of Biostatistics. After randomization, participants will be contacted and informed which randomization assignment they received and scheduled for the intervention. The intervention should begin within four weeks of randomization. Patients who cannot begin the intervention within 30 days of consent (because of conflict or illness), will be placed on a waitlist so they can be offered the intervention when they do not have any conflicts at which time patients will be re-consented.

After the patient has been randomized, they will complete a T1-Baseline Assessment (week 1) before the 1st session (see Appendix C). The assessment battery will be re-administered at 3 subsequent points: T2 (midpoint, at session 4, Appendix D); T3 (post-intervention, following the 7th session of the intervention or at the completion of 14 weeks, whichever occurs first, Appendix E) to assess changes over the course of treatment; and T4 (follow-up, 8-12 weeks post completion of T3, Appendix F) to assess maintenance of treatment gains. The EUC sample will also be administered the battery of questionnaires at approximately equivalent intervals. Please see Appendices A, C, D, E, & F and if it is overly burdensome to come to the counseling center for assessments patients will be given the option to complete them by mail, email the blank questionnaires to participants for them to print and complete at home (forms will be returned by mail), or administer the questionnaires over the phone. Figure 3, section 9.0 for specific measures)

All intervention sessions will be conducted at Ambulatory Counseling Center facilities of the MSKCC Department of Psychiatry and Behavioral Sciences or another Memorial Sloan-Kettering Cancer Center treatment facility. However, in rare circumstances if deemed appropriate by the interventionist (e.g., illness, emergency, transportation difficulties) telephone sessions will be permitted. All psychotherapy sessions will be audio recorded to be used for treatment integrity purposes. Portions of these audio recordings may be transcribed for academic, educational, or

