Enhanced Usual Care (EUC): The use of a usual care condition to increase the methodological rigor of this randomized controlled trial must be balanced with the need for beneficence and preventing harm in the care of patient participants. We are therefore including what we refer to as an —enhanced— usual care arm to this randomized controlled trial to address the ethical issues raised by utilizing a usual care condition in a vulnerable advanced cancer population. The —enhancement— to usual care in this study involves the inclusion of screening and targeted referral components as suggested by Reynolds et al. (2001). Participants will receive feedback about their level of distress (based on the DT administered at screening) and given appropriate targeted referrals based on levels of distress and problem areas endorsed. Participants will be given a letter with a list of appropriate referrals. Several referrals may be made based on identified problem areas, using the following guidelines:

- —Practical Problems—- Social Work on their disease management team
- —Family Problems—- Family Clinic at MSKCC Counseling Center
- —Emotional Problems—- MSKCC Counseling Center
- —Spiritual/Religious Concern—- Pastoral Care Counseling Services
- —Physical Problems—- MSKCC physician or MSKCC Palliative Care Service

In addition, patients may be offered community resources as well. Research assistants conducting the screening and providing feedback and referrals will be trained in the NCCN guidelines for distress management (NCCN, 2009; see Appendix G). Regardless of whether they indicate significant distress or any problem areas patients in the EUC will all be provided with informational brochures on psychosocial services available at MSKCC (i.e., the MSKCC Counseling Center Services Guide for Patients [MSKCC, 2007], psychoeducational materials (see

Appendix H) and a book entitled —The Human Side of Cancer|| by [name]. EUC patients will be closely monitored at each assessment point for significant distress and highly distressed patients (i.e. 8 or above on DT or endorsement of suicidal ideation on BDI) will be referred to the counseling center or contacted by the PI for further assessment as needed.

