Intent-to-treat (ITT) analysis is the gold standard in evaluating the relative efficacy of therapeutic regimes for patients assigned to different treatment arms whether or not they comply with the full treatment plan as defined in the protocol. In contrast to studies that assess clinical outcomes that are observable whether or not patients comply with therapy, it is likely in this study that patients who fail to participate in particular counseling sessions will also be missing the corresponding outcome data. Thus, examination and imputation of incomplete data will be an integral part of our ITT analysis. Data for intermediate time points might be imputable by one of several available statistical techniques. However, it is more problematic to assess outcomes for patients who essentially drop out of the study, namely, who are missing the final (and possibly preceding) evaluations. Although we shall endeavor to obtain final evaluation-time data even for patients who discontinue the counseling, but because of the likelihood that premature withdrawal is related to deteriorating physical health, we cannot rely on this and will therefore use appropriate statistical methods. One preferred approach is the Pattern-Mixture Model (Hedeker & Gibbons, 1997), which assumes that patients can be grouped into a small number of implicit cohorts with different patterns of missing data. This method models the trajectories of responses within each cohort and combines results across cohorts to make overall comparisons between treatment arms. The Pattern-Mixture Model can be relatively easily applied in practice using a publicly accessible SAS macro. This approach will handle two potential, inter-related issues, namely, intent-to-treat analysis and missing data while making a global assessment of the overall efficacy of the two types of counseling. We anticipate that the majority of patients will complete most or all of the planned sessions and the corresponding assessments. However, our pilot data suggest that there may be sufficient attrition to warrant use of the above-described approach even if drop-out rates do not differ significantly between the two treatment arms.

Missing data:

Because attrition may significantly impact the MANOVA, we will utilize several techniques for dealing with missing data (Nich & Carroll, 1997; Singer & Willett, 1991). These techniques may

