include estimating missing data, complete data analysis, and intention to treat analysis. Although missing data can be estimated using a number of powerful techniques (Graham, Hofer, Donaldson, MacKinnon & Schafer, 1997), we intend to use a multiple imputation procedure described by Schafer and Olsen (1997), which is capable of handling categorical data, continuous data, and any combination of the two. Graham et al. (1997) have argued that parameter estimates using this method are unbiased and have standard errors that are typically only slightly larger than those generated by other methods. In order to assess the effect of this imputation method, we will compare results based on imputed data to those based only on subjects who completed the study (this comparison allows for an assessment of the extent to which biases may have influenced study results). Finally, we can analyze data assuming that those subjects who dropped out of treatment had no change in either meaning or psychological distress.

Procedures to control False Discovery Rate (FDR):

One final issue is that of multiple statistical analyses. While the use of MANOVA models decreases the possibility of inflated type I error normally observed when several outcome measures are being evaluated, analysis of the individual dependent variables can also incorporate a multiple comparisons method, such as a the False Discovery Rate-controlling procedure (Benjamini & Hochberg, 1995).

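### The optional no-change sensitivity analysis is tied to leaving treatment rather than to a missing T3, so it is undefined for EUC, could overwrite observed data and does not test worsening

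*Combined protocol and SAP*

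**What the plan says.** All of the missing-data text is in section 11.0.

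- Under Missing data, multiple imputation is the intended method, with a comparison against completers. The paragraph then adds that "we can analyze data assuming that those subjects who dropped out of treatment had no change in either meaning or psychological distress". No arm is named and leaving treatment is not defined.
- Under Intent-to-treat analyses, the plan describes a different group: "patients who essentially drop out of the study, namely, who are missing the final (and possibly preceding) evaluations". It promises that "we shall endeavor to obtain final evaluation-time data even for patients who discontinue the counseling", but does not rely on this "because of the likelihood that premature withdrawal is related to deteriorating physical health". A pattern-mixture model is named there as a preferred approach.
- Just before the sample size text, T2 is to stand in for patients too sick to finish the seven sessions.

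For EUC, section 4.3 describes referrals, brochures and a book: "Participants will be given a letter with a list of appropriate referrals". Section 4.2 keeps EUC on the outcome schedule: "The EUC sample will also be administered the battery of questionnaires at approximately equivalent intervals".

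**The concern.** A sensitivity analysis for attrition should apply to the patients whose outcome is missing, treat all arms alike, and cover a scenario at least as bad as the one feared. This one falls short on each count.

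1. **Trigger.** Leaving treatment and lacking T3 are different events. EUC patients can be lost to assessment but have no sessions to drop out of, so the rule does not say what happens to them. IMCP versus EUC is one of the two a priori contrasts.
2. **Observed data.** T3 is due after session 7 or at 14 weeks, whichever comes first (sections 4.2 and 7.1). A patient who stops counseling can therefore still provide it. The sentence makes no exception for such values.
3. **Scenario.** If health is declining at withdrawal, no change from baseline may be a kind assumption. No listed analysis explicitly places drop-outs below baseline.

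At stake is whether this analysis, if reported, says anything reliable about the robustness of the result to attrition.

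**Working it through.** **Does the trigger cover EUC?** The intent-to-treat text defines study drop-out by missing evaluations, while the no-change sentence uses treatment drop-out. The same section refers to two types of counseling and two treatment arms, and section 4.3 reserves the term treatment conditions for IMCP and ISP. The natural reading is the session-based arms, which leaves EUC undefined.

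**Inputs**
- Share set to no change, d = 25%, from the sample size text. Check: 1 − 104/138 = 24.6%, and 138 × 0.75 = 103.5, consistent with 104 of 138 retained. The plan does not split attrition by arm and gives no figure for the no-change analysis itself.
- True mean worsening of drop-outs, w = 0.2 to 0.5 SD. This is an assumption; the documents give no value.
- Mean change in those who stay: m in a therapy arm, mE in EUC (positive = better).

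**One therapy arm**
- True mean change = (1 − d)m − dw.
- Mean under the rule = (1 − d)m + d × 0.
- Overstatement = dw: 0.25 × 0.2 = 0.05 SD; 0.25 × 0.3 = 0.075 SD; 0.25 × 0.5 = 0.125 SD.

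**IMCP minus EUC, with equal d and w in both arms**

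| Handling of missing EUC outcomes | Net bias | At d = 25% |
|---|---|---|
| True worsening retained (limiting case) | +dw | +0.05 to +0.125 SD |
| Imputed to resemble EUC completers | dw − d(mE + w) = −d·mE | mE = −0.2: +0.05; mE = 0: 0; mE = +0.2: −0.05 SD |
| No change in EUC as well | dw − dw | 0 |

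The sign therefore turns on something the plan does not state.

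**Is a symmetric no-change rule enough?** Only if drop-out is equal. Two removal criteria in section 10.0, intolerance of the intervention and non-compliance with it, fit mainly the session arms, so unequal loss is plausible. With an assumed 25% against 15%, the residual is (0.25 − 0.15) × w: 0.02 SD at w = 0.2 and 0.05 SD at w = 0.5. Such a rule also still leaves worsening untested.

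**IMCP minus ISP.** The rule covers both arms, so the bias is dw − dw = 0 when drop-out and worsening are equal.

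**Overlap with the T2 rule.** A patient too ill to finish counseling meets the T2 substitution and may also count as having left treatment. One rule assigns the T2 score and the other the baseline score. No precedence is given.

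**The case against.** The strongest reply is that this is one optional analysis, listed last, and loosely worded rather than wrong. It sits under a missing-data heading in a plan committed to intention to treat, so a sensible analyst would apply it only where T3 is absent. The statistics section introduces the trial as one to "compare the efficacy of three psychotherapy interventions", so treatment might loosely include EUC. The T2 substitution and the pattern-mixture model also address withdrawals, and the latter lets drop-outs differ from completers.

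Much of this stands. Overwriting is a literal reading, not a declared intention, and this is not the plan's only handling of withdrawals. But the loose label does not say what leaving EUC treatment would mean, and a pattern-mixture model shows worsening only as far as observed trajectories reveal it.

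A reader might go further and infer that the rule favours IMCP over EUC. The documents do not support that:
- The sentence names no arm, and the sign depends on EUC handling, as shown above.
- Against imputation from improving completers, no change lowers the therapy mean. With an illustrative gain of 0.5 SD and 25% missing, the drop is 0.25 × 0.5 = 0.125 SD.
- The deterioration the plan names is physical; worse meaning or distress is an extrapolation.
- The pilot's 20 of 59 (33.9%) who missed at least one IMCP session is not a missing-T3 rate, and the same pilot account claims full delivery to over 90%. Neither figure is a sound value for d.
- The 0.20 standardized difference in the sample size text is stated for IMCP versus ISP, so it is not a yardstick for a bias in IMCP versus EUC.

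**Conclusion.** The point holds as a defect of specification in an optional sensitivity analysis. As written, the rule is undefined for EUC, does not protect T3 values observed after counseling stops, and does not examine outcomes worse than baseline. The overstatement of a therapy-arm mean is 0.05 to 0.125 SD, conditional on 25% being set to no change and on an assumed true worsening of 0.2 to 0.5 SD. No direction can be assigned to the net effect on IMCP versus EUC. On IMCP versus ISP, which the plan calls the more important comparison, the effect cancels under equal drop-out and worsening. The main analysis is not affected. The change is worth making because it is cheap and gives a more informative check.

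**What to change.** Replace the no-change sentence with a pre-specified analysis along these lines:

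- It applies to patients in any arm with no T3 value, whatever their session attendance.
- Starting from the multiple imputations already planned, their T3 scores are shifted toward worse over a stated range, for example 0.2, 0.3 and 0.5 SD, with the worse direction defined for each scale.
- The shift is applied first equally in all three arms and then in IMCP only.
- Observed T3 values are always used, including those obtained after counseling stops.
- The text states how this relates to the T2 substitution, and which takes precedence when both could apply.

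The shift sizes are examples; what matters is that the range is fixed in advance. The cost is a change of wording and a few extra runs. The downside is that the sensitivity result may be less favourable to IMCP.
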